		
individual outcomes. Instead, we focused on identifying the minimum detectable effect size at 80% power and 5% significance level. Given that this is a pilot study, our primary objective is to analyze data with the specific intent of establishing population parameters and estimating effect sizes.
 
Modified power calculations indicate that with a sample size of 40, we will have the ability to detect a minimum standardized difference (Cohen's d) of 0.9 with adequate power (80%) at a 5% significance level. The reduced sample size will still allow us to make meaningful conclusions regarding feasibility and estimation of effect sizes. To obtain a final sample size of $n = 40$, we are looking to enroll $n = 50$ participants to account for a potential 20% dropout or non-completion rate.

8	5/3/2023	
Revision of the informed consent process to include the option of using e-consent for completion of the informed consent form and electronic signature of consent by study team members obtaining verbal informed consent.
 
Revision of data collection procedures to note that study activities and collection of data points will be completed whenever possible given participants' underlying condition and because this is a pilot study.

9	11/9/2023	
Revision of the study protocol to include a projection to enroll $n = 70 - 90$ participants, instead of $n = 50$ participants, to obtain a final sample size of $n = 40$.
 
The previous version of the protocol included a projection to enroll $n = 50$ participants, accounting for a potential 20% drop-out or non-completion rate, to obtain a final sample size of $n = 40$. However, the observed rate of drop-out or non-completion was more than double the potential estimate. Therefore, more individuals need to be enrolled to try to achieve a final sample size of $n = 40$.

Table of Contents

1.	Study Summary.....	3
2.	Objectives.....	3
3.	Background.....	4
4.	Study Endpoints.....	9
5.	Study Intervention/Investigational Agent.....	10
6.	Procedures Involved	12
7.	Data and Specimen Banking.....	15
8.	Sharing of Results with Participants.....	15
9.	Study Timelines.....	15
10.	Inclusion and Exclusion Criteria.....	16
11.	Vulnerable Populations.....	17
12.	Local Number of Participants.....	17
13.	Recruitment Methods.....	17
14.	Withdrawal of Participants.....	18
15.	Risks to Participants.....	18
16.	Potential Benefits to Participants.....	21
17.	Compensation to Participants.....	22

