week, VR, mind-body approach to daily management of chronic pain that is designed for home use. Similar to in-person integrative pain management programs, EaseVRx provides therapeutic information to support participants in learning cognitive and behavior self-management skills, and retraining the pain pathways. The program incorporates pain education, pain psychology, biofeedback training to control breathing, relaxation based on mindfulness-based stress reduction (via 360-degree videos), and distraction via interactive games. Program modules are presented in a Netflix-style format. In a RCT of EaseVRx versus audio control in adults with chronic low back pain or fibromyalgia (\geq age 18, n = 97), 76% of the VR users reported no nausea or motion sickness and 83% reported high satisfaction ratings.⁴⁰ VR resulted in significant improvement in average pain intensity ($p=0.036$), pain-related inference with activity ($p=0.005$), sleep ($p<0.001$), mood ($p<0.001$), and stress ($p=0.003$). Symptom improvement, over time, was found for each pain variable ($p<.001$) with stronger results strengthening after two weeks. These findings support the feasibility and efficacy of using EaseVRx for chronic pain.

For adults with SCD, VR therapies may be more efficacious and result in fewer complications than opioid therapy. Thus, they can contribute to cost savings for the healthcare infrastructure. However, EaseVRx has not been tested in SCD. Moreover, the findings of our ongoing systematic review investigating the use and efficacy of VR in chronic pain conditions indicate that, to date, there have been no published studies of VR interventions for chronic pain management for adults with SCD. In addition, currently available VR pain self-management tools are designed for a generic or majority audience. Trials of EaseVRx in SCD are needed to evaluate the feasibility and establish the efficacy of using VR-based therapies to manage chronic pain in Black adults with SCD. In addition, studies are needed to determine how these therapies can be revised to be culturally-tailored for a target audience of predominantly Black individuals. This study will address all of these gaps.

Preliminary data and study models

In conjunction with the literature, the preliminary work conducted by the PI forms the basis for this research.

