Primary feasibility measures will include enrollment and randomization, engagement, study retention, satisfaction, and safety. Secondary feasibility measures related to participants' satisfaction will include program fit with daily activities, barriers to use, and areas of program confusion or misuse. We will estimate the following parameters to determine whether the intervention shows promise for further investigations to determine its efficacy: 1) enrollment and randomization; 2) dropout or non-completion rate; 3) completion rate of baseline, mid-treatment, and post-treatment assessments; 4) completion rate of weekly VR modules and daily self-report assessments; 5) participant engagement and satisfaction; 6) rate of adverse effects (primary safety endpoint); and 7) participants' perceptions of the content, delivery, and tailoring required. Data collection methods will include program usage statistics (automatically recorded by the VR program), completion of study assessments, and qualitative sessions to collect subjective data. EaseVRx usage data will be surveyed monthly for the duration of the intervention.

Aim 2 – To assess the preliminary efficacy of EaseVRx on pain and pain-related outcomes among adults with SCD.

Outcomes of preliminary efficacy are pain, pain coping, sleep, functional activities of daily living, disability, healthcare utilization, and QOL. Pain coping outcomes are pain catastrophizing, chronic pain acceptance, chronic pain self-efficacy, health literacy, executive function, anxiety, depression, and social support. The pre-specified primary outcome is pain coping, and the primary measure of pain coping is pain catastrophizing. Data collection methods will include (also see the Schedule of Activities):

Demographics questionnaire

Adult Sickle Cell Quality of Life Measurement Information System (ASCQ-MeSM) SCD Medical History Checklist⁵²⁻⁵⁴

Medical record data collection form

Pain diary

Chronic Pain Grade Questionnaire⁵⁵

Pain Catastrophizing Scale^{56,57}

Chronic Pain Acceptance Questionnaire⁵⁸

Chronic Pain Self-Efficacy Scale⁵⁹

BRIEF Health Literacy Screening Tool^{60,61}

Behavior Rating Inventory of Executive Function ®—Adult Version (BRIEF-A)^{62,63}

PROMIS® Emotional Distress – Anxiety⁶⁴

PROMIS® Emotional Distress – Depression⁶⁴

Social Support Questionnaire⁶⁵

ASQ-MeSM Short Forms: Sleep Impact, Pain, Pain Episodes, Emotional Distress, Social Functioning, and Stiffness⁵²⁻⁵⁴

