After the treatment period, we will retrieve study materials and conduct the qualitative sessions. Of the participants, we will randomly select approximately 50% ($n = 10$) from the VR group and approximately 50% ($n = 10$) from the control group for the qualitative sessions to learn about participants experiences with the treatment program and preferences for pain coping strategies. We may conduct individual interviews in participants' homes or focus groups sessions in a private area of the sickle cell clinic or research office, or may utilize remote options if necessary or if requested by participants.

[figure not shown]
Data Collection Procedures

Using quantitative and qualitative sources, data collection will occur at baseline, daily, mid-treatment (week 4), and post-treatment (week 8 and follow-up at week 12). Quantitative sources will include survey instruments, a daily pain diary, and electronic medical record review. Qualitative sources will include individual, semi-structured interviews or focus group sessions. Participants' electronic medical records will be reviewed, concurrently with data collection, for demographics, medical history, clinical data, analgesic and non-analgesic medications, and healthcare utilization. After group allocation at baseline, research activities will be conducted remotely in an effort to conceal treatment allocation.

Given the nature of sickle cell disease and individual disease experiences, we anticipate that participants may not be able to complete all study activities or provide data at all time points throughout the study. Because this is a pilot study, study activities and collection of data points will be completed whenever possible.

Study Schema

Study Measures and Schedule of Activities

The valid and reliable survey instruments that will be used to collect study data are described in Table 1. All data will be collected via direct entry into REDCap or another online data management system that can be accessed using a computer or smartphone. Participants will receive a link to complete the electronic surveys and pain diary after baseline data collection.

Table 1. Study Measures and Schedule of Activities

Study Outcomes	Measures (see attached documents)	Data Collection (*W = Week)				
		Baseline	Daily (Day 1 – 56)	W4 (Day 28)	W8 (Day 56)	W12 (Day 84, Follow-up)
Demographics	Demographics questionnaire	x				

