	Adult Sickle Cell Quality of Life Measurement Information System (ASCO-Me SM) SCD Medical History Checklist	x				
	Medical record data collection form	x				
Pain and self-management of pain	Pain diary	x	x	x	x	x
Pain and disability	Chronic Pain Grade Questionnaire	x		x	x	x
Pain catastrophizing	Pain Catastrophizing Scale	x		x	x	x
Chronic pain acceptance	Chronic Pain Acceptance Questionnaire	x		x	x	x
Chronic pain self-efficacy	Chronic Pain Self-Efficacy Scale	x		x	x	x
Health literacy	BRIEF Health Literacy Screening Tool	x		x	x	x
Executive function	Behavior Rating Inventory of Executive Function ®—Adult Version (BRIEF-A)	x		x	x	x
Anxiety	PROMIS® Emotional Distress - Anxiety	x		x	x	x
Depression	PROMIS® Emotional Distress - Depression	x		x	x	x
Social support	Social Support Questionnaire	x		x	x	x
Sleep	ASCO-Me SM Sleep Impact Short Form	x		x	x	x
Functional activities of daily living	ASCO-Me SM Pain Short Form	x		x	x	x
Quality of life	ASCO-Me SM Short Forms: Pain Episodes, Emotional Distress, Social Functioning, Stiffness	x		x	x	x
Screening prior to treatment	Questionnaire to Screen for Cybersickness or Digital Motion Sickness	x				
	Virtual Reality Sickness Questionnaire		x	x	x	
Participant engagement and acceptability	Program usage statistics (automatically recorded by the VR program) and completion of study questionnaires		x	x	x	
Study retention	Program usage statistics (automatically recorded by the VR program) and completion of study questionnaires	x	x	x	x	x
Participant satisfaction, and participant needs and preferences for tailoring the program	Semi-structured interview guide for qualitative sessions					x

7. Data and Specimen Banking

Not applicable

8. Sharing of Results with Participants

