will be employed. Additionally, all analyses will include sex (male vs female) as a biological variable to assess differences in outcomes within each group.

Number and percent will be used to summarize the primary feasibility measures while content analysis will be used to summarize the secondary feasibility measures. Optimal treatment will be determined by correlations among the engagement outcomes and measures of preliminary efficacy. We will use mixed-effects models to test whether the outcomes differ across the treatment group over time (from pre- to post intervention). Depending on the type of outcome (continuous or categorical), linear or generalized mixed effects models will be used, respectively. In this approach, each participant is treated as an experimental unit with repeated observations over time. The model will include fixed effects of time, intervention group, and time x intervention group interaction, and assume an unstructured variance-covariance matrix to describe the covariance structure. We will adjust for any baseline group differences in participant characteristics. A significant interaction effect will indicate significant differences in outcomes by treatment groups over time. We will select the most parsimonious model using Akaike information criterion (AIC) and Bayesian information criterion (BIC). Hypotheses tests based on specific contrasts in the mixed model and the interaction term between time and intervention group will be performed to test whether subjects in the intervention group demonstrated improved outcomes compared to the control group. The model-based estimates of the outcome measures for the two treatment groups at each time point will be used to estimate effect sizes for future studies.

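### Satisfaction, a primary feasibility measure to be reported as number and percent, has as its only listed source a week 12 interview held with about half of each arm

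*Combined protocol and SAP*

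**What the plan says.** Section 4, Aim 1, sets the measures: "Primary feasibility measures will include enrollment and randomization, engagement, study retention, satisfaction, and safety". The same paragraph puts engagement and satisfaction among the parameters used to judge whether the intervention merits further study. It treats program fit, barriers and areas of confusion as separate, secondary measures.

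Section 18, Data Analysis, fixes the summaries: "Number and percent will be used to summarize the primary feasibility measures while content analysis will be used to summarize the secondary feasibility measures". Interview data are then assigned to content analysis with a codebook.

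Table 1 in Section 6 has one row for satisfaction, shared with needs and preferences for tailoring. Its instrument is "Semi-structured interview guide for qualitative sessions", marked in the week 12 column only.

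Section 6, Procedures for Participants, says who is interviewed: "Of the participants, we will randomly select approximately 50" percent of each arm, given as n = 10 in each. The sessions may be individual interviews or "focus groups sessions in a private area of the sickle cell clinic or research office", with remote options. Section 4, Aim 3, lists satisfaction among the interview topics.

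**The concern.** The plan promises a count and a percent for satisfaction but lists no source that would produce them for the whole trial. The one listed source is a semi-structured conversation with a subsample, and its stated analysis is the method that Section 18 assigns to the secondary measures. If the sessions are focus groups, individual answers are harder to separate and count.

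Feasibility is Aim 1, so this percent is one of the results the pilot exists to deliver. Section 3 also cites an earlier randomized trial of the same program in which "83% reported high satisfaction ratings", and readers will naturally set the new figure beside that one. A percent from about 10 people per arm would be too imprecise for the comparison to say much.

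**Working it through.** **Step 1. Can another listed source supply the percent?** The nearest other Table 1 row is engagement and acceptability. Its sources are automatic usage records and completion of questionnaires, neither of which asks whether a participant was satisfied. No survey named in Section 4 or Table 1 is described as measuring satisfaction. Table 1 refers to attached documents that were not available, so a closed rating item inside the interview guide cannot be ruled out. If there is one, it reaches only those selected for a session.

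**Step 2. Reproduce the plan's interview number.** The final sample is 40 with 1:1 allocation (Section 6).
- Per arm: 40 / 2 = 20.
- Half of that: 0.50 × 20 = 10, as stated.

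So the stated percentage and n = 10 agree only for 20 per arm. The 20 people interviewed in total are 20/90 = 22% to 20/70 = 29% of the 70 to 90 to be enrolled.

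**Step 3. Precision of the percent.** The documents give no expected satisfaction rate for this trial. I assume 80%, close to the 83% cited in Section 3. The intervals are exact (Clopper-Pearson) 95% limits: for x of n, the 2.5% quantile of Beta(x, n − x + 1) and the 97.5% quantile of Beta(x + 1, n − x).

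| Who answers, per arm | Count | 95% interval | Width (points) |
|---|---|---|---|
| 10 interviewed | 8/10 | 44.4% to 97.5% | 53 |
| All 20 completers | 16/20 | 56.3% to 94.3% | 38 |

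**Step 4. Noise from interviewing only half of the completers.** Suppose 16 of 20 completers are satisfied and 10 are drawn at random. The number satisfied in the draw is hypergeometric: P(k) = C(16, k) × C(4, 10 − k) / C(20, 10).

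| Satisfied among 10 | 6 | 7 | 8 | 9 | 10 |
|---|---|---|---|---|---|
| Probability | 0.043 | 0.248 | 0.418 | 0.248 | 0.043 |

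- Off by exactly 10 points (7 or 9): 0.248 + 0.248 = 0.496, about 50% of draws.
- Off by more than 10 points (6 or 10): 0.043 + 0.043 = 0.086, about 9% of draws.

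With 10 people, 10 points is the smallest error possible short of being exactly right. The distribution is symmetric about 8, so the draw adds noise and no bias. Asking all 20 removes this component.

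**Step 5. The other reading of half.** If the percentage is applied to enrolled participants, an equal split of 70 to 90 gives 35 to 45 per arm. Half is 17.5 to 22.5, taken as 18 to 22. The counts nearest 80% give:
- 14/18: 52.4% to 93.6%, width 41 points.
- 18/22: 59.7% to 94.8%, width 35 points.

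These are close to the 38 points for 16/20, so on this reading most of the precision gain from asking all completers disappears.

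**The case against.** The strongest reply is that this is an exploratory mixed-methods pilot. Interviewing a random half is a legitimate way to study satisfaction. No threshold or go/no-go rule for satisfaction is stated, and both 44% to 97% and 56% to 94% are wide. One could reconcile Section 4, Table 1 and Section 18 on paper, or simply report the interview denominator. Much of this stands: the gain in precision is moderate, and it depends on what the stated half refers to. What it does not answer is that the plan classes satisfaction as primary and promises a percent, while a fixed question to everyone would cost almost nothing.

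Three stronger readings are tempting, and the documents do not support them.

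- **That no rating item exists.** The guide was not available, so only the limited reach of the interviews can be asserted.
- **That the half-sample gives a wrong answer in most draws.** Adding the two figures in Step 4 gives 58%, but that means only that the result is not exactly 8 of 10. Errors above 10 points occur in about 9% of draws.
- **That the percent is biased because about half of participants are lost.** Enrolling 70 to 90 to end with 40 implies 1 − 40/70 = 43% to 1 − 40/90 = 56%, and the version 9 entry says "the observed rate of drop-out or non-completion was more than double the potential estimate". Those figures combine dropout with non-completion. Section 6 says "we anticipate that participants may not be able to complete all study activities or provide data at all time points throughout the study", so a non-completer may still be in the study and may be selected for interview. The share actually withdrawn is not given, nor is the satisfaction of those who stop, so neither the size nor the direction of any bias can be stated.

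**Conclusion.** The point holds as a mismatch between a primary measure's planned summary and its only listed source. Followed as written, the plan yields a satisfaction percent from about 10 people per arm, in sessions that may be group discussions and whose stated analysis is not a count.

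Under an assumed 80% satisfaction and 20 completers per arm, the exact 95% interval is 53 points wide with the interviews and 38 points wide if all completers answer. That comparison rests on the stated n = 10; if half means half of those enrolled, little of the difference in width remains. On either reading, the percent still comes from a subsample interview and not from a question listed for all participants. No claim of bias is made. The change is worth making because it is cheap, and the point does not threaten the rest of the trial.

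**What to change.** Add one or two fixed satisfaction rating items to the existing week 8 REDCap survey, for all participants in both arms, with a matching row in Table 1. Word them to suit both the headset and the audio program, and state in advance which responses count as satisfied. Report number and percent per arm from these items, with the denominator and the number not answering. Keep the week 12 sessions for the qualitative findings.

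The cost is one or two minutes on a survey that Section 13 puts at 45 minutes (1/45 = 2.2% to 2/45 = 4.4%), plus a protocol modification. No visit is added.

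The limits should be stated openly. The trial was already under way at version 9, so participants past week 8 when the change takes effect will lack the item. Those withdrawn before week 8 will not answer, because Section 14 ends data collection at withdrawal. The percent therefore describes week 8 responders and should be labeled so. Asking the same items at an exit contact, before withdrawal takes effect, is an option but is not needed for the fix.

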After screening patients for eligibility using the inclusion and exclusion criteria, the project coordinator will describe the study to and seek participation from eligible individuals. Participants will be informed that the purpose of the study is to test a pain management intervention that will be delivered in two different ways, but their group allocation will not be revealed. The study conditions will be presented as adjuncts to standard care and there will be no restriction on using other pain management methods. After patients provide written, informed consent or verbal informed consent, they will complete baseline study questionnaires. Once enrolled, participants may self-withdraw at any time, or they may be withdrawn if they fail to or are unable to comply with study procedures. In that case, recruitment will resume and continue until the target number of participants is reached.

After completing baseline questionnaires, participants will be randomized 1:1 to receive either EaseVRx or control. Only individuals meeting the eligibility criteria for VR will be assigned to the VR group. Participants will receive study materials and instructions for home use before being followed prospectively for 8-weeks with follow-up at 12 weeks. Participants in the VR group will receive an all-in-one, non-tethered VR headset (Pico G24K headset with AppliedVR breathing amplifier) that is pre-loaded with EaseVRx. They will receive education and hands-on experience with the VR headset to ensure safe and comfortable device use at home. Access to technical support will also be provided. Each week, participants will be asked to complete 7 assigned modules, averaging 5 minutes in duration and ranging from 2 to 16 minutes in

Protocol Title: Home-Based Intervention for Chronic Pain in Adults with Sickle Cell Disease (HIPAS)

duration, for a total of 56 modules across the program. The order of the modules is fixed but participants can repeat modules as desired. Participants in the control group will be asked to use the audio only version of EaseVRx, which excludes references to visual content, to complete 7 sessions weekly. They will receive an electronic link to the recordings on SoundCloud (a music streaming platform) where they can choose to stream or download the audio recordings on their smartphone, laptop, or desktop computer.

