The James R. Clark Sickle Cell Memorial Foundation (SC Memorial Foundation) is not engaged in this research. The Foundation will serve as a community-based, recruitment site through which potential participants will be contacted and informed about the study. Emory study staff will coordinate, in person or remotely, recruitment and participant onboarding activities for potential participants identified through the SC Memorial Foundation.

The participant burden is estimated to be 45 minutes at each time point for surveys, 2 hours weekly of intervention for 8 weeks, and 1 hour for qualitative sessions. Participants will receive \$50 after baseline, \$50 after each 4-week study period (\$150 in total), and \$50 after the qualitative sessions.

14. Withdrawal of Participants

Data collection will be monitored daily by the study team. Participants will be sent a reminder text or email if they do not submit data after 4 days. If no response is received after 2 days, a team member will conduct a telephone call. We will use a maximum of 3 attempts to contact participants. If 2 weeks have passed since last data submission and contact attempts have been unsuccessful, the participant will be considered lost to follow-up and will be withdrawn from the study. Before making this determination, we will try to regain contact with the participant (via 3 telephone calls and, if necessary, a certified letter mailed to the participant's last known address). These attempts will be documented in the participant's study file.

We may conclude an individual's participation in this study without their consent for any reason, especially if we believe it is in their best interest or if they were to object to any future changes that may be made in the study plan. Expected reasons for conclusion of participation may include:

- Experiencing any symptoms of cybersickness or digital motion sickness (such as dizziness, lightheadedness, issues with balance, nausea, and/or vomiting) during or after exposure to VR
- Experiencing severe mental distress

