If participants do not finish any portion of the study, then they will be compensated for the portion(s) they have completed and will no longer have their data collected after they have withdrawn from the study. Data that were already collected may still be used for this study as we try to understand pain in individuals with sickle cell and develop interventions. If participants would like us to discontinue use of their data after they withdraw from the study, then they will contact the principal investigator, at

the mailing address provided, with a written request. Once we receive the written request, their data will be destroyed.

15. Risks to Participants

Potential Risks

This study involves minimal risk, if any. Exposure to VR may result in an infrequent physical risk of cybersickness or digital motion sickness. In addition, we will solicit information regarding participants' pain and disease experiences. Therefore, there is a potential, likely, infrequent psychological risk because discussion of these experiences might result in emotional distress and/or embarrassment to the participants. There may also be rare, social risks in that there may be social harm (i.e., stigmatization) to the participant and larger community of individuals with SCD. A breach of confidentiality may result in social consequences such as being perceived negatively by healthcare providers, family members, or employers. Economic consequences may also arise if individuals need to choose an alternate healthcare provider because of a breach of confidentiality. This alternate healthcare provider may be in another county or state. Accordingly, the participant may incur costs for transportation and/or care.

Procedures to Reduce Risks

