use period, we will use telephone calls or text messages to conduct weekly study assessments of adverse events. Users of the VR program who experience adverse events are free to suspend or halt VR use at any time by removing the headset. This can remedy the VR side effects. In addition, the VR program offers a range of experiences to allow participants to identify lower risk experiences. For participants who experience adverse events, we will discontinue their study participation and refer them to a member of the medical team as needed for any medical follow-up. All participants will have the ability to withdraw from the study at any time.

At this time, the risks of VR during pregnancy (i.e., risks to the pregnant woman, the embryo, or fetus) are not yet known. Therefore, to protect against possible side effects, women who are pregnant or nursing a child will not participate in exposure to VR. Female participants will be asked to immediately notify study staff if they become pregnant during the study. In that case, they will not be exposed to VR but may continue with other remaining study activities.

Active suicidal ideation, as documented in the patient's medical records, is one of the exclusion criteria. Among eligible participants, we will assess depression with the PROMIS® Emotional Distress – Depression (Short Form) at baseline, mid-treatment, and monthly post-treatment via remote data collection. This measure does not include a suicide item. To manage participants who score in the upper range of the depression measure or disclose suicidal ideation, we will utilize the following protocol.

- a. At the end of the survey in the questionnaire management system, participants will see this statement: *If you are feeling distressed or you are having thoughts of hurting yourself, please call 911, call the 24-hour Georgia Crisis and Access Line at [name], call the South Carolina 24-hour Crisis Response Dispatcher at [name], go to Grady Memorial Hospital or your local hospital, or call your healthcare provider.*

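### A team stop for severe mental distress appears also to end outcome collection, an avoidable gap in intent-to-treat follow-up (minor)

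*Combined protocol and SAP*

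**What the plan says.** Section 14 lets the team end someone's participation without that person's consent. Among the expected grounds it lists "Experiencing severe mental distress", with no scale, threshold or assessor. The wording is permissive: the team may stop someone, and is not obliged to.

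The paragraph after that list, still in Section 14, says that people who do not complete the study "will no longer have their data collected after they have withdrawn from the study". Data already collected may still be used unless the person asks in writing for their destruction.

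Four other places bear on this:

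- Section 6, Data Collection Procedures, says that "study activities and collection of data points will be completed whenever possible".
- Section 15, Procedures to Reduce Risks, says: "For participants who experience adverse events, we will discontinue their study participation". For pregnancy the same section separates treatment from follow-up: "they will not be exposed to VR but may continue with other remaining study activities".
- Section 15 also sets a pathway for severe depression scores (PROMIS T above 70) and disclosed suicidal ideation. It leads to referral and to the participant's own choice about continuing.
- Section 18, Data Analysis, specifies intent-to-treat, REML estimation, an evaluation of attrition, and a sensitivity analysis for missing data whose method is not given.

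**The concern.** Stopping the intervention for someone in distress is legitimate. The difficulty is that the protocol does not separate stopping the intervention from stopping measurement. Under intent-to-treat, a randomised person's outcomes are wanted whether or not the person stays on the programme. Here they are lost by rule, possibly from someone willing to give them.

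The reason for the stop is also close to what is measured. Section 4 names pain catastrophizing as the primary measure of pain coping and counts anxiety and depression among the pain coping outcomes. If people are removed because they are distressed, the scores that go missing may be the worse ones. Section 4 also makes dropout or non-completion a feasibility parameter, and unless stops are recorded by reason, team decisions are mixed with participants' own dropout.

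**Working it through.** **1. Does the data rule cover team stops?** The Section 14 sentence does not name them, so this is a reading. Two places use the same word for removal by the team:

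- Section 6, Procedures for Participants: "participants may self-withdraw at any time, or they may be withdrawn if they fail to or are unable to comply with study procedures".
- Section 14, on non-response: "the participant will be considered lost to follow-up and will be withdrawn from the study".

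The data rule directly follows the list of team-initiated grounds. The natural reading is that it applies to them, and no other text keeps outcome follow-up for a person stopped for distress.

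**2. Loss per stop.** Table 1 in Section 6 schedules pain catastrophizing, anxiety, depression and the emotional distress form at baseline and weeks 4, 8 and 12. A stop before week 4 loses 3 of 3 post-baseline assessments, between weeks 4 and 8 it loses 2, and between weeks 8 and 12 it loses 1.

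**3. Scale against planned attrition.** Section 12 enrols 70 to 90 to finish with 40.

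- Expected loss: 70 − 40 = 30 (30/70 = 42.9%) to 90 − 40 = 50 (50/90 = 55.6%).
- One stop as a share of enrolment: 1/90 = 1.1% to 1/70 = 1.4%.
- One stop as a share of the expected loss: 1/50 = 2.0% to 1/30 = 3.3%.

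Nothing in the protocol says how much of that loss is due to distress.

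**4. The plan's detectable difference.** The revision history gives d = 0.9 for a final 40 at 80% power and two-sided 5%. With 20 per arm, a two-sample t-test gives a minimum detectable d of 0.909 (power 79.2% at d = 0.9), so the figure reproduces. A stop for distress does not change it, because Section 6 resumes recruitment after withdrawals until the target number is reached.

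**5. Possible bias.** The following are assumptions, not protocol figures:

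- PROMIS Depression mean T of 55 to 60, SD 9, baseline T at most 70, and no true change.
- Correlation between visits of 0.6 to 0.7.
- Correlation of depression with pain catastrophizing of 0.4 to 0.6.
- T above 70 as a stand-in for the undefined ground. The protocol does not link the two.

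The week 8 mean is estimated by likelihood, regressing sequentially on baseline and week 4, in simulations of 800,000 people per setting.

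If the stop follows a score already recorded, the bias is about 0, because the model conditions on that score. If it follows distress disclosed between visits (T above 70 at week 2 or 6, not on a questionnaire), the bias depends on the share of such people who are stopped:

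| Share stopped | Gone before week 8 | Depression T too low by | Pain catastrophizing too low by |
|---|---|---|---|
| 10% | 0.6–1.7% | 0.02–0.06 | 0.001–0.004 SD |
| 25% | 1.5–4.3% | 0.06–0.16 | 0.003–0.010 SD |
| 50% | 2.8–8.1% | 0.11–0.32 | 0.005–0.021 SD |
| 100% (upper bound) | 5.3–14.9% | 0.23–0.66 | 0.010–0.040 SD |

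Section 15 calls the psychological risk infrequent, so the lower shares are more plausible. The upper bound is 0.0098/0.9 = 1.1% to 0.0404/0.9 = 4.5% of the detectable difference. It reaches the contrast between arms in full only if every stop falls in one arm.

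**The case against.** The strongest objection is that continued questioning may do harm. Section 15 says of pain and disease experiences that "discussion of these experiences might result in emotional distress and/or embarrassment to the participants". It names no psychological risk from the programme itself, which includes relaxation and mindfulness content. Ending the programme while still offering 45-minute surveys could therefore remove the helpful part and keep the upsetting part. This stands as a limit on the remedy. It is why the questionnaires should be an offer, with a clinical pause. Section 15 already lets participants decline any question.

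A second objection is that the plan handles much of this. Section 19 reviews withdrawals monthly, and Section 18 plans REML, an attrition evaluation and a sensitivity analysis. That is largely right. What is missing is a tabulation of team stops by arm and reason, without which the sensitivity analysis has little to work from.

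A third is that cybersickness, the ground listed beside distress, follows VR exposure and so falls in one arm, and that the adverse-event sentence in Section 15 is mandatory where Section 14 is not. Both points are fair, and the same wording should cover them.

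A reader might also infer that Section 14 contradicts the Section 15 pathway for severe scorers. It does not. The Section 14 power is discretionary, its ground is not equated with a severe depression score, and a person can be offered the choice to continue under Section 15 without any conflict arising.

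**Conclusion.** The point holds as a minor one. Read naturally, Section 14 turns a discretionary stop for distress into an end of outcome collection, which sits poorly with intent-to-treat and with the stated wish to collect data where possible. The cost is one to three missed post-baseline assessments per person stopped.

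Three stronger conclusions are tempting and unsupported:

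- **That this rule explains the 43–56% loss.** The protocol attributes none of that loss to distress, and the number of such stops cannot be derived.
- **That it shrinks the final sample or worsens the detectable difference.** Recruitment resumes to reach the target. Replacement restores numbers but does not supply the missing outcomes of the people stopped.
- **That it materially biases the result.** On the assumptions above the bias in pain catastrophizing is 0.001–0.010 SD when 10–25% of such people are stopped, and at most 0.040 SD.

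The conclusion rests on reading the Section 14 data rule as covering team stops. If the sponsor intends otherwise, a sentence saying so settles the main point.

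**What to change.** In Section 14, state that a team-initiated stop for mental distress ends the intervention only. The week 4, 8 and 12 remote questionnaires stay on offer to willing participants, unless paused on recorded clinical grounds. Leave the data rule unchanged for people who withdraw themselves.

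Align the adverse-event sentence in Section 15 with this, so that distress recorded as an adverse event does not bring back the full stop. The same wording can sensibly cover the cybersickness ground. The pregnancy rule shows that the protocol already accepts such a separation.

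Within the withdrawal review planned in Section 19, tabulate team stops by arm and reason, and use the table in the Section 18 sensitivity analysis.

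The cost is protocol and consent wording with IRB review. For a distressed participant it is at most three voluntary surveys (3 × 45 = 135 minutes), with the 3 × $50 = $150 already foreseen for the three 4-week periods. Questions may add to distress; the clinical pause protects against that and gives back part of the gain. Sample size and analysis model do not change.
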